6.2.a. ω-3 fish oil and placebo (corn oil) are obtained by Epax in 0.7 g gel caps and they have identical shape, color, taste and weight. Each 0.7 g of fish oil ω-3 contains 400 mg eicosapentaenoic acid (EPA) and 200 mg docosahexaenoic acid (DHA). We start with 1.4 g/day of fish oil and continue until the 6 month visit. If the average of IL-6 measured at 3- and 6-month visits does not **decrease by ≥40%** vs. baseline (average of screening visits 1 and 2), we increase the dose to 2.8 g/day. To limit the effect of within subject variation, we use the average of 2 measures. If there is an acute illness within one month prior to the visit, the 3-month or the 6-month IL-6 measure is postponed or excluded from titration algorithms. In previous RCTs, ω-3 reduced IL-6 by >50% using 1 to 2 g/day of fish oil.^{75, 76} In other trials in elders, fish oil was used in comparable doses

ranging from 0.6 to 2.3 g/day.⁶²

6.2.a.1. Risks and risk protection and dose adjustments related to administration of ω -3

There are no contraindications to the use of ω -3 fish oil, except intolerance or allergy to fish oil. ω -3 are considered very safe and produce only mild adverse effects involving gastrointestinal upset and fishy aftertaste.^{148, 149} FDA has affirming menhaden fish oil as **Generally Recognized As Safe (GRAS)** under 21 CFR 4 184.1472 provided that the daily intake of EPA and DHA combined do not exceed 3 g per person per day. <http://www.accessdata.fda.gov/scripts/cdrh/cfdocs/cfcfr/CFRSearch.cfm?fr=184.1472> and <http://www.fda.gov/Food/IngredientsPackagingLabeling/GRAS/SCOGS/default.htm> accessed on 9/11/2014.

ω -3 may rarely cause clinical or subclinical bleeding, worsening of glycemic control in people with impaired glucose tolerance, rise in LDL cholesterol, and possibly hypotension when combined with antihypertensive treatment.

We start with a dose of 1.4 g/day of ω -3 fish oil. Adverse effects, such as gastrointestinal discomfort are monitored. Dose will be adjusted as below based on serum glucose, LDL cholesterol and hemoglobin measured at baseline and at month 3, 6, and 9. ω -3 fish oil dose will be decreased or discontinued if any of the following criteria are met at follow-up:

- New onset paroxysmal or persistent atrial fibrillation
- Hemoglobin decreases by $\geq 20\%$ from baseline (dose will be discontinued),
- The participant is not diabetic and fasting glucose is > 126 AND has increased by $>30\%$ from baseline,

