6.3. Safety dose titration. ARBs produce blood pressure reductions similar to those seen with ACE inhibitors and other antihypertensive classes. These drugs vary in efficacy and duration of action but all are recommended for once daily dosing. Like ACE inhibitors, duration of antihypertensive effects is dose-dependent; therefore, smooth blood pressure control over 24 hours is most likely at the maximum recommended dose. To avoid precipitous initial fall in blood pressure or decline in renal function, we start therapy with the lower dose of losartan (25 mg/day). If there are no safety concerns, the dose is increased to 50 mg/day and safety is again checked in about 1 week. To identify abrupt reduction in renal function that warrants drug dose reduction and to avoid dangerous hyperkalemia, we measure eGFR, potassium, and blood pressure before and soon (approximately 1 week) after starting losartan and after any dose adjustment. However, dose adjustments downward that are not related to renal function or hyperkalemia will not require a short-term follow-up blood draw.

In general, losartan dose will be maintained if ALL of the following criteria are met:

- Blood pressure is $\geq 100/50$ and $< 110/50$,
- Potassium < 5.5 ,
- eGFR has NOT declined by $\geq 20\%$ from baseline, and
- No symptoms of lightheadedness or dizziness.

Losartan dose will be decreased if ALL of the following criteria are met:

- Blood pressure is $\geq 90/50$ and $< 100/50$,
- Potassium < 5.5 ,
- eGFR has NOT declined by $\geq 20\%$ from baseline, and
- No symptoms of lightheadedness or dizziness.

Losartan dose will be stopped if ANY of the following criteria are met:

- Blood pressure $< 90/50$,
- Potassium ≥ 5.5 ,
- eGFR decline $\geq 20\%$ from baseline, or
- Symptoms of dizziness, lightheadedness, or syncope.

The principal investigator/study physician at each site has discretion to alter the losartan titration schedule on a case by case basis.

We increase the dose of losartan to 100 mg/day if the average of IL-6 measured at 3- and 6-month visits is not **decreased by at least 40%** vs. baseline (average of screening visits 1 and 2). The 40% threshold

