was selected based on previous trials with ARBs. ARBs have been shown to reduce IL-6 by >40%^{77, 78} and by 58%⁷⁹ in RCTs, and to be consistent with the threshold used above for ω -3 fish oil. To minimize the impact of outliers due to acute illness, the 3-month or the 6-month IL-6 measure are excluded or postponed if there is acute illness within one month prior to the visit.

As part of the safety monitoring of the ENRGISE interventions, we measure blood pressure, blood hemoglobin, serum glucose, eGFR, LDL cholesterol, and potassium at baseline and at 3, 6, and 9 months of follow-up. In addition for those in the losartan arm of the trial, blood pressure, serum potassium, and eGFR, are measured about 1 week after randomization and about 1 week after any losartan dosage adjustment. However, serum potassium and eGFR are not measured one week after a downward dose adjustment that was not based on potassium or eGFR values.

6.4. The Investigational New Drug (IND) Per requirement of the Institutional Review Board, #IND124103 was submitted and approved by the FDA with the mention “STUDY MAY PROCEED”

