Frailty is a state of increased vulnerability to endogenous and exogenous stressors.^{169, 170} Frailty involves fatigue, weight loss, infections, balance, strength and gait impairment leading to an increased risk of falls, delirium, and disability. In addition frailty is associated with inflammation⁴³ and thus it may be averted by anti-inflammatory interventions. We characterize frailty with Fried criteria developed by Fried et al. that employ self-reported exhaustion, unintentional weight loss, low energy expenditure, slow gait speed, and weak grip strength.¹⁷¹ Those with ≥3 of the 5 factors are judged to be frail, those with 1 or 2 factors as pre-frail, and those with no factors as non-frail.

Isometric hand grip strength is a commonly used measure of upper body skeletal muscle function and has been widely used as a general indicator of functional status.^{172, 173} Higher IL-6 levels are associated with lower grip strength.^{3, 7, 174} Thus, reducing IL-6 with LO and ω-3 may result in higher grip strength vs. placebo. Grip strength in both hands is measured as we have successfully applied in LIFE.¹⁶²

Isokinetic dynamometry of the knee extensors and flexors.

Participants complete this measure at baseline and 12 months. Observational studies have shown associations between knee extension isokinetic strength and physical functioning, disability and mortality.¹⁷⁶ The reliability of this measure is generally excellent.^{177, 178} In addition, several randomized trials in older mobility limited populations have shown this measure to be responsive to therapeutic interventions.^{179, 180}

The Short Form (SF-36) Health Survey¹⁸¹⁻¹⁸⁴ is administered to assess the general health status as

Table 6.3. Schedule of screening, assessments and follow-up procedures in the pilot trial

Visit type	Phone scr.	Scr. visit 1	Scr. visit 2	Base. Visit	Safety*	3-Mo visit	Safety*	6-Mo visit	Safety*	9-Mo visit	Safety*	12-Mo visit	Safety*	Extra visit**
Basic eligibility screening	x													
Short consent and 4 m walk test		x												
IL-6		x	x			x ^{&}		x ^{&}		x ^{&}		x ^{&}		
Medical history			x											
MMSE			x											
Safety blood tests			x	x	x	x	x*	x	x*	x	x*		x*	x
Additional biomarkers				x		x		x				x		
Vital signs			x	x	x	x	x	x	x	x	x	x	x	x
Anthropometric measures				x		x		x		x		x		
Main Informed consent				x										
Physical performance measures			x	x		x		x		x		x		
Medical history update & adverse events				x	x	x	x	x	x	x	x	x	x	x

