Questionnaires				x								x		
Dispense study drugs				x		x		x		x				
Assess compliance						x		x		x		x		
Proxy interview (if needed)						x		x		x		x		

* BP, and serum potassium and eGFR are measured about 1 week after the LO dose adjustment (potassium and eGFR are not measured if LO dose is reduced only for BP values). ** Extra visits if there are safety concerns. & The IL-6 measure is excluded or postponed if there has been an acute illness within one month prior to the visit.

Participant Reported Outcomes (PRO).

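### No scheduled safety panel after month 9, although the top doses start only after the 6-month IL-6 and treatment runs to month 12; the gap is widest for fish oil

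*Combined protocol and SAP*

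**What the plan says.** **Panel schedule.** Section 6.3 lists blood pressure, hemoglobin, glucose, "eGFR, LDL cholesterol, and potassium at baseline and at 3, 6, and 9 months of follow-up". Section 6.2.a.1 bases fish oil dose adjustment on "serum glucose, LDL cholesterol and hemoglobin measured at baseline and at month 3, 6, and 9". In Table 6.3 the row "Safety blood tests" has an unconditional mark at screening visit 2, baseline, the first safety visit and months 3, 6 and 9. Its 12-month cell is blank. IL-6 and additional biomarkers are drawn at month 12.

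**Dose escalation.** For fish oil, Section 6.2.a says: "We start with 1.4 g/day of fish oil and continue until the 6 month visit". The dose then goes to 2.8 g/day if the mean of the 3- and 6-month IL-6 has not fallen by at least 40%. For losartan, Section 6.3 applies the same rule: "We increase the dose of losartan to 100 mg/day if the average of IL-6 measured at 3- and 6-month visits is not" reduced by that amount. Either IL-6 measure may be excluded or postponed after an acute illness, and no maximum delay is given.

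**Treatment period.** Follow-up is one year (Section 6.1). Table 6.3 has drug dispensed at baseline and months 3, 6 and 9, and compliance assessed up to month 12.

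**Other checks.** The Table 6.3 footnote says "BP, and serum potassium and eGFR are measured about 1 week after the LO dose adjustment", except that potassium and eGFR are omitted after a reduction made only for blood pressure. Conditional bloods (x*) are marked in the safety columns after months 3, 6, 9 and 12. There are also "Extra visits if there are safety concerns", which carry safety bloods.

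**The concern.** Scheduled testing stops three months before treatment does, and those months are top-dose time for anyone who has been escalated. The protocol itself names bleeding, worse glycemic control, LDL rise, hyperkalemia and renal impairment as risks (Sections 6.2.a.1 and 6.2.b.1). Several of these can be silent and show only in the laboratory. Aim a(iii) requires the pilot to assess the dosage and safety of the interventions, and Section 6.10.e makes safety part of the decision on what goes into the main trial. The doses with the least laboratory follow-up are the highest ones tested.

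The end of Table 6.3 is also unclear. It marks x* bloods after the 12-month visit and ties them to a losartan dose adjustment, although at that visit no drug is dispensed and no safety blood is taken.

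**Working it through.** The plan gives no figure of its own on this point, so the check has three parts.

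**1. Is the blank cell real?** Table 6.3 has 14 visit columns, and the safety blood row has 14 cells. Aligned one to one, the 12-month cell is empty. The text of Sections 6.2.a.1 and 6.3 independently stops at month 9, so this is not an artefact of how the table was read.

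**2. Timeline.** For escalation at month *s*, top-dose time is 12 − *s*; exposure at the month-9 draw is max(0, 9 − *s*); exposure after the last scheduled panel is 12 − max(9, *s*).

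| Escalation at month | Top-dose months | Months on top dose at month-9 draw | Months after last panel | Share after last panel |
|---|---|---|---|---|
| 6 | 6 | 3 | 3 | 50% |
| 7 | 5 | 2 | 3 | 60% |
| 8 | 4 | 1 | 3 | 75% |
| 9 | 3 | 0 | 3 | 100% |

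The lower dose has full panels at months 3 and 6, and the top dose at most the one at month 9. For fish oil that is the only scheduled glucose, LDL and hemoglobin test after escalation, and it misses the top dose altogether only if escalation falls at or after that draw. Losartan adds blood pressure, potassium and eGFR about a week after the increase.

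**3. How many would be escalated?** Inputs: within-person CV of 30% (Section 6.2.a.1), two baseline and two follow-up IL-6 values, and a 40% threshold. On a lognormal model the SD of one log value is √ln(1 + 0.30²) = 0.294. The SD of the log ratio of two 2-value means is 0.294 × √(1/2 + 1/2) = 0.294. For a true proportional reduction *r*,

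P(trigger met) = 1 − Φ{[ln 0.60 − ln(1 − *r*)] / 0.294}.

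| True IL-6 reduction | Source of the value | Share meeting the trigger |
|---|---|---|
| 0% | no effect | 95.9% |
| 10% | power section, 6.10.b | 91.6% |
| 15% | power section, 6.10.b | 88.2% |
| 20% | power section, 6.10.b | 83.6% |
| 40% | titration threshold | 50.0% |
| 50% | fish oil trials cited (given as above 50%) | 26.7% |
| 58% | one ARB trial cited | 11% |

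The last row is 1 − Φ(0.357/0.294) = 1 − Φ(1.21). A simulation with arithmetic rather than geometric means gave 91.5% and 83.4% at 10% and 20%, so the range for the power-section effects is about 83 to 92%. If the CV is assumed to be 20% or 40% instead, the 15% case becomes 96% or 82%. These shares ignore regression to the mean and any participant held back for safety.

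**The case against.** The strongest reply is that the text and table agree on months 3, 6 and 9, so this is a deliberate schedule. Section 6.2.a.1 ties the fish oil tests to dose decisions, and at month 12 there is no further dose to decide. That holds for dosing. It does not dispose of the point, because Section 6.3 presents the same panel as safety monitoring of the interventions, and the pilot has to report on safety.

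Four stronger readings are tempting, and the documents do not support them:

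- **All safety bloods end at month 9.** Only the scheduled panel does. Conditional potassium and eGFR draws and extra-visit bloods remain.
- **Top-dose safety rests on one draw or none for both drugs.** This is wrong for losartan potassium and eGFR, which are checked about a week after escalation as well as at month 9 if escalation came earlier.
- **Fish oil at 2.8 g/day is never tested.** This needs escalation at or after the month-9 draw. Postponement has no stated limit, but the documents do not describe IL-6 turnaround or say that a new dose must wait for the next dispensing visit. It is an assumption.
- **Late problems are neither found nor followed up.** Vital signs and adverse events are collected at month 12, and the DSMB can request more safety data (Section 7.5). What lacks scheduled detection is a silent laboratory change.

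The objection on size also stands. The 10 to 20% effects are differences used for power, whereas the titration rationale cites reductions above 40%, so it is not established that most participants end on the top dose. Likewise, 135 assigned per drug × 0.25 year = 33.75 person-years covers everyone assigned, including those not escalated, stopped or lost. It is not top-dose exposure.

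**Conclusion.** The point holds as a gap in scheduled laboratory monitoring. The last 3 of 12 treatment months (25%) have no scheduled panel; for someone escalated at month 6 this is half of top-dose time, and more if escalation is later. It weighs most for fish oil, whose dose increase has no linked laboratory check. The share affected runs from about 11% to about 92% of treated participants as the true IL-6 reduction goes from 58% to 10%, given a 30% CV, lognormal variation, no regression to the mean and no safety bar to escalation. Separately, no stated event at the 12-month visit would trigger the x* bloods marked after it. The fault is worth correcting because it limits what the pilot can say about laboratory safety at its highest doses. It does not affect the efficacy analyses.

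**What to change.** Reconcile Table 6.3 and Sections 6.2.a.1 and 6.3 with the 12-month treatment period so that laboratory safety data cover the last quarter of treatment. Blood is already drawn at month 12 for IL-6 and biomarkers, which would allow the existing panel to be run there without a new visit. State what the x* after the 12-month visit refers to. Report laboratory changes by the dose in use at each draw, so that top-dose results are not merged with those on lower doses. Thresholds, triggers and any treatment action remain with the sponsor's physicians.

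Cost: one routine panel for about 300 people, a protocol amendment, and one extra breakdown in the safety tables.

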6.5. Compliance

To measure compliance with LO and ω -3, we use dual methods involving both pill count¹⁵² and participant recall.¹⁵³ Pills are counted at each study visit.

6.6. Recruitment – inclusion/ exclusion criteria - (details in Table 6.2.)

We identify men and women aged ≥ 70 years who are **able to complete the 400 m walk** at baseline, and are at **high risk of mobility disability** assessed by

- Self-reported difficulty walking ¼ mile or climbing a flight of stairs,
- Usual walking speed <1 m/sec and >0.44 m/sec on the 4 m walk (in the pilot phase we explore the feasibility of recruiting at least 50% of participants who have a baseline walking speed of <0.80 m/sec and >0.44 m/sec),^{22, 154, 155} and
- Chronic low-grade inflammation measured by IL-6 >2.5 pg/ml, the threshold we have found for increased risk of mobility limitation,^{1, 2} and <30 pg/ml to exclude high grade inflammation. To minimize within person variability,^{150, 156} IL-6 is the average of 2 measures taken at screening visits, with the first measure being >2.3 and <30 pg/ml, and the average of the two measures >2.5 and <30 pg/ml.

We exclude subjects with acute, autoimmune and HIV illnesses and causes of low walking speed that may be related to neurological conditions, severe arthritis, or low vitamin D. Other exclusion criteria reflect conditions that may interfere with the conduct of the study, interventions or assessments. Those taking ACEI or ARB are excluded from the LO randomization and those eating >2 servings/week of fish in the past year or taking fish oil are excluded from the ω -3 randomization. We recruit from the community. We use recruitment strategies successfully applied in LIFE,¹⁵⁷ LIFE-Pilot,¹⁵⁸ and TTrial,¹⁵⁹ which include primarily mass mailing, and newspaper, radio and TV ads and explore alternative recruitment strategies, such as electronic medical records to identify patients not taking study drugs and assess whether that strategy is effective in lieu of or in addition to mass mailing.

Table 6.2. Inclusion and exclusion criteria

Inclusion Criteria
 
 • Men and women age ≥ 70 years • Self-reported difficulty walking ¼ of a mile or climbing a flight of stairs • Walking speed <1 m/sec and >0.44 m/sec on the 4 m walk at usual pace. A walking speed of ≤ 0.44 m/sec would not be compatible with completing the 400 m walk in 15 min. (In the pilot phase we explore the feasibility of recruiting at least 50% of participants who have a baseline walking speed of <0.80 m/sec and >0.44 m/sec) • Able to complete the 400 m walk test within 15 minutes without sitting or the help of another person and without a walker, a cane is allowed • Blood level IL-6 >2.5 pg/ml and <30 pg/ml. • Willingness to be randomized to the intervention groups

Exclusion criteria
 
 • Failure or inability to provide informed consent • Lives in a nursing home; persons living in assisted or independent housing are not excluded • Self-reported inability to walk one block

- Significant cognitive impairment, defined as a known diagnosis of dementia, or a Mini-Mental State Exam (MMSE) score <24 (<23 for racial/ethnic minorities or participants with less than 9 years of education)
- Unable to communicate because of severe hearing loss or speech disorder
- Neurological conditions that are causing impaired muscle function or mobility (may include stroke with residual paresis, paralysis, neuropathy, Parkinson disease, or multiple sclerosis)
- Severe rheumatologic or orthopedic diseases, e.g., awaiting joint replacement, known active inflammatory or autoimmune disease (e.g. rheumatoid arthritis, lupus, Crohn's disease, HIV)
- Terminal illness with life expectancy less than 12 months
- Severe pulmonary disease, requiring either steroid pills or injections
- Other significant co-morbid disease that in the opinion of the field center PI would impair ability to participate in the trial, e.g. renal failure on hemodialysis, severe psychiatric disorder (e.g. bipolar, schizophrenia), excessive alcohol use (>14 drinks per week); drug addiction; treatment for cancer (radiation or chemotherapy) within the past 1 year; or other conditions
- Lives outside of the study site or is planning to move out of the area in next 1 year or leave the area for >3 months during the next year
- Exclusion criteria that apply only to those who receive losartan:
 - Intolerance or allergy to ARBs
 - Known bilateral renal artery stenosis or liver cirrhosis
 - Hypotension SBP<110 or DBP<60 mmHg
 - Serum potassium ≥5.0 mEq/L
 - Use of lithium salts
 - eGFR < 15
 - Congestive heart failure with ejection fraction < 40%
- Exclusion criteria that apply only to those who receive ω-3:
 - Intolerance or allergy to ω-3 or fish/shellfish
 - Fatty fish intake >2 servings per week on average
 - History of paroxysmal or persistent atrial fibrillation
- To maintain blinding, those who are not eligible to receive any active treatment (ω-3 or losartan) are excluded

Temporary exclusion criteria

- Myocardial infarction, CABG, or valve replacement within past 6 months;
- Pulmonary embolism or deep venous thrombosis within past 6 months;
- Uncontrolled diabetes with recent weight loss, diabetic coma, or frequent insulin reactions;
- Stroke, hip fracture, hip or knee replacement, or spinal surgery within past 4 months;
- Physical therapy for gait, balance, or other lower extremity training within the past 2 months;
- Severe hypertension, e.g., SBP > 200, or DBP > 110 mmHg;
- Hemoglobin <10 g/dL
- Participation in another intervention trial within 3 months; participation in an observational study may be permitted;
- Current smoking (within 6 months),
- Acute infection (urinary, respiratory, other) or hospitalization within 1 month
- Exclusion criteria that apply only to those who receive losartan:
 - Use of ACEI, ARB within 2 months
 - Use of aliskiren within 2 months in patients with type 2 diabetes or renal impairment with eGFR<60¹⁶¹
 - Use of potassium sparing diuretics, other medications with potassium sparing properties (such as but not limited to spironolactone or eplerenone), potassium supplements, and salt substitutes containing potassium within 1 week
 - Transaminases >twice upper limit of normal to exclude participants with impaired liver function
- Exclusion criteria that apply only to those who receive ω-3:
 - Use of ω-3 within 2 months

To maintain blinding, those who are not eligible to receive any active treatment (ω-3 or losartan) are excluded

6.7. Outcomes

6.7.a. Primary Outcomes

IL-6 and walking speed during the 400 m walk test are the main outcomes of the pilot study as outlined below.

The 400 m walk test at usual pace is used.¹⁴³ **Major mobility disability (MMD)**,^{143, 162} defined as inability to walk ¼ mile or 400 m, is measured in the pilot study and is our preferred primary outcome for the main trial. MMD is of major public health significance. Ability to walk ¼ mile is measured in the US census¹⁶³ and in most epidemiologic surveys.¹⁸ The MMD outcome based on the 400 m walk test is a feasible, objective, reliable,¹⁶⁴ well-validated and important clinical and public health outcome in older people,^{22, 143, 162} which has been

successfully implemented in the LIFE-Pilot and LIFE.^{165, 166} We have shown it to be a more efficient outcome for clinical trials than self-reported disability or the Short Physical Performance Battery (SPPB).¹⁶⁷ Public health agencies use ability to walk ¼ mile or 400 m to define need and policy impact of interventions.¹⁸ Finally, people reporting the inability to walk 400 m incur higher health care costs of \$4,000 per person per year, compared with those not reporting inability to walk 400 m.¹⁸⁻²² MMD is operationalized as the inability to complete a 400 m walk test within 15 min without sitting or help of another person or walker.¹⁶² Completing the walk in >15 min would be in an extremely slow pace (<0.45 m/sec), which is of little utility in daily life.¹⁶⁸ A higher cut point (30 or 60 min), makes the assessment impractical and does not add to the clinical significance of the outcome. The time to walk 400 meters and the ability to complete the test provide data to test effects of the interventions resulting from both attenuation of decline and increase in walking speed. We hypothesize that the interventions reduce the risk of reaching the MMD outcome.

Non-completion of this test can be addressed by adjudicating MMD based on objective inability to walk 4 m in ≤10 sec, or self- or proxy-reported inability to walk across a room.

6.7.b. Secondary and exploratory outcomes and measures

SPPB. A low score on the SPPB based on 4 m walk, balance & chair stands tests is a risk factor for disability, institutionalization, morbidity and mortality in initially non-disabled older persons.¹⁻³ The summary score and components of the SPPB have good reliability (ICCs range from 0.88 to 0.92).^{4,5}

Frailty is a state of increased vulnerability to endogenous and exogenous stressors.^{169, 170} Frailty involves fatigue, weight loss, infections, balance, strength and gait impairment leading to an increased risk of falls, delirium, and disability. In addition frailty is associated with inflammation⁴³ and thus it may be averted by anti-inflammatory interventions. We characterize frailty with Fried criteria developed by Fried et al. that employ self-reported exhaustion, unintentional weight loss, low energy expenditure, slow gait speed, and weak grip strength.¹⁷¹ Those with ≥3 of the 5 factors are judged to be frail, those with 1 or 2 factors as pre-frail, and those with no factors as non-frail.

Isometric hand grip strength is a commonly used measure of upper body skeletal muscle function and has been widely used as a general indicator of functional status.^{172, 173} Higher IL-6 levels are associated with lower grip strength.^{3, 7, 174} Thus, reducing IL-6 with LO and ω-3 may result in higher grip strength vs. placebo. Grip strength in both hands is measured as we have successfully applied in LIFE.¹⁶²

Isokinetic dynamometry of the knee extensors and flexors.

Participants complete this measure at baseline and 12 months. Observational studies have shown associations between knee extension isokinetic strength and physical functioning, disability and mortality.¹⁷⁶ The reliability of this measure is generally excellent.^{177, 178} In addition, several randomized trials in older mobility limited populations have shown this measure to be responsive to therapeutic interventions.^{179, 180}

The Short Form (SF-36) Health Survey¹⁸¹⁻¹⁸⁴ is administered to assess the general health status as

Table 6.3. Schedule of screening, assessments and follow-up procedures in the pilot trial

Visit type	Phone scr.	Scr. visit 1	Scr. visit 2	Base. Visit	Safety*	3-Mo visit	Safety*	6-Mo visit	Safety*	9-Mo visit	Safety*	12-Mo visit	Safety*	Extra visit**
Basic eligibility screening	x													
Short consent and 4 m walk test		x												
IL-6		x	x			x ^{&}		x ^{&}		x ^{&}		x ^{&}		
Medical history			x											
MMSE			x											
Safety blood tests			x	x	x	x	x*	x	x*	x	x*		x*	x
Additional biomarkers				x		x		x				x		
Vital signs			x	x	x	x	x	x	x	x	x	x	x	x
Anthropometric measures				x		x		x		x		x		
Main Informed consent				x										
Physical performance measures			x	x		x		x		x		x		
Medical history update & adverse events				x	x	x	x	x	x	x	x	x	x	x
Questionnaires				x								x		
Dispense study drugs				x		x		x		x				
Assess compliance						x		x		x		x		
Proxy interview (if needed)						x		x		x		x		

* BP, and serum potassium and eGFR are measured about 1 week after the LO dose adjustment (potassium and eGFR are not measured if LO dose is reduced only for BP values). ** Extra visits if there are safety concerns. & The IL-6 measure is excluded or postponed if there has been an acute illness within one month prior to the visit.

Participant Reported Outcomes (PRO).

